7.6.1. Demographics and Baseline Characteristics

The following characteristics will be summarized for participants in each treatment group and each cohort (i.e., ITT, mITT and PP): age, sex, years since PD diagnosis, levodopa equivalent daily dose (LEDD) at start of treatment (Jost, Kaldenbach et al. 2023), race and ethnicity.

7.6.2. Disease characteristics

Baseline Hoehn & Yahr scores will be summarized. Additionally, motor phenotypes (i.e., tremor-dominant, postural instability gait difficulty and intermediate) classified based on the Baseline 2 visit MDS-UPDRS part II and part III scores and previously-established methodology (Stebbins, Goetz et al. 2013). Specifically, a Tremor score will be calculated by summing all items from 2.10, 3.15, 3.16, 3.17 and 3.18 from the MDS-UPDRS. A postural instability and gait difficulty (PIGD) score will be calculated by summing all items from 2.12, 2.13, 3.10, 3.11 and 3.12 from the MDS-UPDRS. Ratios of Tremor score/PIGD score will be used to classify motor phenotypes. Ratios $\geq 1.15 =$ Tremor dominant. Ratios $\leq 0.90 =$ PIGD dominant. Scores > 0.9 and < 1.15 = intermediate. If data required to calculate the scores is missing from the Baseline 2 visit, data from the Baseline 1 visit will be analyzed. Post randomization data will not be considered. Classification will only be performed on complete case data.

7.6.3. Pre-study and Concomitant Medications

The number and percentage of each treatment group on concomitant therapies at randomization will be reported categorically including the following:

- adenosine A2A antagonists
- amantadine
- anticonvulsants
- anti-depressant/antianxiety medications
- antiemetics
- antihistamines
- antihypertensives
- antipsychotics
- central anticholinergics
- cognitive enhancers
- COMT Inhibitors
- contraceptives
- corticosteroids
- dystonia treatments
- incontinence treatments
- inhaled levodopa
- inhaled or ingested cannabinoids
- laxatives/stool softeners
- MAO-B inhibitors
- narcotics
- oral or transdermal dopamine agonists
- oral levodopa-based therapies
- oral levodopa-based therapies/COMT inhibitors
- orthostatic hypotension treatments

- pain/cramping treatments
- pump therapies
- sexual dysfunction treatments
- sialorrhea treatments
- sleep aids
- stimulants
- other

Changes in medications to treat symptoms associated with PD during the trial are a protocol deviation. Changes in these medications would exclude participants from the PP analysis and will be determined prior to unblinding of treatment allocation. Changes in medications used to treat symptoms associated with PD and change from baseline to end of treatment in LEDD will be summarized descriptively for the mITT and the ITT populations.

Certain concomitant medications (e.g., antihistamines, central anticholinergics or acetylcholinesterase inhibitors) may alter treatment efficacy by affecting neurotransmitter systems involved in the mechanisms of action for tvCVS. Sensitivity analyses will be performed to compare treatment effects in study participants taking these concomitant medications during the trial against study participants that did not take these concomitant medications.

7.6.4. Study Device Administration

Treatment adherence will be analyzed after the database lock for the RCT. Treatment adherence data will be reported descriptively. Treatment adherence $\geq 70\%$ of the expected randomized treatments over the duration of the treatment period will be required for inclusion in the PP analysis (see section 7.1).

7.7. EFFICACY ANALYSIS

Efficacy will be determined using (Zeger and Liang 1992, Zorn 2001) a linear regression utilizing a mixed effects (i.e., mixed model repeated measures [MMRM]). This approach allows for repeated measurements on a subject (i.e., all time points during the study) and unequally spaced as well as missing data (dropouts or intermittent), allows for the inclusion of continuous or categorical covariates, allows for a flexible specification of the covariance structure. This modeling technique has been shown to produce unbiased estimates in the case of data missing at random. Additionally, the MMRM estimation is robust to departures from normality. (Rubin 1987)

The following MMRM model (Zeger and Liang 1992, Zorn 2001) will be analyzed to determine significance for the primary endpoint:

$$\begin{split} Y_{ij} &\sim N(0, \sigma^2) \\ Y_{ij} &= \beta_0 + \beta_1 * ARM_i + \beta_2 * VISIT_{ij} + \beta_3 * ARM_i * VISIT_{ij} + \beta_4 * SITE_i \\ & \text{where:} \end{split}$$

 $Y_{ij} = (MDS_NMS \text{ total score for participant i at time } j) - (MDS_NMS \text{ total score for})$

participant i at baseline),

 $ARM_i = 1$ if participant i is in the treatment arm

= 0 if participant i is in the passive arm,

 $VISIT_{ij}$ = an ordinal variable representing the visit for j^{th} measurement for

participant i

SITE_i is a nominal variable indicating the site for participant i,

An unstructured covariance structure will be utilized for the R matrix. The Kenward-Roger approximation will be used to estimate the denominator degrees of freedom. The difference between active and passive treatment at each visit will be estimated based on the Least Squares Mean (LSMean) difference between the treatment groups at the visit from the MMRM with the associated 90% confidence interval (CI) and 1-sided P-value. Additionally, the p-value for the site effect will be presented. If the unstructured covariance matrix results in convergence issue, the heterogeneous Toeplitz covariance structure followed by the heterogeneous first-order autoregressive (AR(1)) structure will be used. In these cases, sandwich estimators will be obtained from the model fitting procedure to ensure unbiased estimation of the treatment effect.

Note: The VISIT effect will be included only when there are multiple post-randomization assessments for a given endpoint. In those cases, a significant interaction between ARM and VISIT will determine a statistically significant finding at a given VISIT. An effect for baseline value will be included for outcomes where the baseline scores significantly different between the treatment arms.

In cases where there is a single post-randomization assessment for a given endpoint, the linear model fit will be simplified to:

$$\begin{split} Y_i &\sim N(0, \sigma^2) \\ Y_i &= \beta_0 + \beta_1 * ARM_i \ + \beta_2 * SITE_i \end{split}$$

where:

 $Y_i = (Endpoint assessment for subject i) - (Endpoint assessment for$

participant i at baseline),

 $ARM_i = 1$ if participant i is in the treatment arm

= 0 if participant i is in the passive arm,

SITE_i is a nominal variable indicating the site for participant i,

The difference between active and passive treatment will be estimated based on the Least Squares Mean (LSMean) difference between the treatment groups from the linear model with the associated confidence interval (CI) and P-value. Additionally, the p-value for the site effect will be presented.

An effect for baseline value will be included for outcomes where the baseline scores significantly different between the treatment arms.

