Participants receiving active treatment also demonstrated significant improvements in motor function according to the MDS-UPDRS II, MDS-UPDRS III and the TUG. All participants in the single-site RCT study were taking stable doses of DRTs. MDS-UPDRS motor exams were conducted by a single rater who was blind to treatment allocation, and all assessments were performed at a consistent interval from the last DRT dose in the case of oral DRTs.

For both motor and non-motor symptoms, additional benefits were demonstrated in the second 4 weeks (28 days) of treatment relative to the first, and the clinical effects in the PD study were durable (i.e., stable one-month post-treatment). Allocation guess data from this study indicated that participants remained blind to treatment allocation.

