7.8. EFFICACY ANALYSIS

⁷Analysis of continuous endpoints will be conducted utilizing the methodology as described in section 7.7 of the SAP v6.0 for RCT Study (Appendix 1). For comparisons within the passive-active arm, the visit variable will be based on the adjusted analysis visit for the active comparisons and the subject effect of the model will be nested within ARM to account for the crossover nature of these data. For efficacy endpoints that have a baseline defined, only participants who have baseline data collected for the endpoints will be included in efficacy analyses.

7.8.1. Primary Objectives:

The primary objective is to further evaluate the effectiveness of TNM[™] Device treatments to reduce non-motor symptom burden in PD for the purposes of supporting reimbursement and clinical adoption.

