7.8.4.1. Combined measure of MDS-UPDRS Parts I, II, and III (sum score)

This endpoint will evaluate the change in the combined measure of MDS-UPDRS Parts I, II and III. The combined measure of MDS-UPDRS Parts I, II, III will be calculated, inclusive of imputation, as described in SAP v6.0 for RCT Study (Appendix 1). For the passive-active group, the change from corresponding baseline to end of treatment

period will be evaluated using a MMRM model similar to the one described for the primary analysis. Treatment differences will be assessed based on the least-squares mean change scores between the passive and active treatments. Changes meeting or exceeding the previously established MCID for this measure (-6.7 points for clinical improvement)⁸ will be considered clinically meaningful.

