7.7.1. Primary Endpoint

The primary endpoint is the change in MDS-NMS total score at the end of the treatment period (day 113) relative to baseline (mean of day 0 and day 29) scores.

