7.7.1.1. Statistical Significance

The null hypothesis is TNMTM Device treatments will yield an equivalent change in NMS burden in the two treatment arms. The alternative hypothesis is that the active treatment arm will do better than (be superior to) the passive treatment arm. The threshold to determine statistical significance will be set at $\alpha = 0.05$ based upon a 1-tailed test⁴.

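### RCT SAP 7.7 lets a significant ARM-by-VISIT interaction decide significance at a visit; that is not a test of the day-113 treatment difference

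*SAP*

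**What the plan says.** RCT SAP 7.7 fits an MMRM to change from baseline with terms for ARM, VISIT, ARM*VISIT and SITE and an unstructured covariance matrix. It then describes two routes to a conclusion.

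- **Visit contrast.** "The difference between active and passive treatment at each visit will be estimated based on the Least Squares Mean (LSMean) difference" between the groups, with a 90% confidence interval and a 1-sided p-value. Section 7.7.1 sets the primary endpoint at day 113, and section 7.7.1.1 tests superiority at 0.05 "based upon a 1-tailed test".
- **Interaction.** The Note below the model says that, where there are several post-randomization assessments, "a significant interaction between ARM and VISIT will determine a statistically significant finding at a given VISIT".

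VISIT is defined as "an ordinal variable representing the visit for" each measurement, with a single coefficient for the interaction.

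The OLE SAP (7.8) analyses continuous endpoints "utilizing the methodology as described in section 7.7 of the SAP v6.0 for RCT Study". Its sections 7.8.4.1 and 7.8.4.2 nevertheless say: "Treatment differences will be assessed based on the least-squares mean change scores between the passive and active treatments".

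**The concern.** The two routes answer different questions, and the RCT SAP neither ranks them nor calls the interaction supportive. The Note uses deciding language and covers the primary endpoint (MDS-NMS at days 57, 85 and 113). It also covers MDS-UPDRS II and PDQ-39SI (days 56, 84 and 112).

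Under the hierarchy in 7.7.2, the primary result opens the way to all five secondary endpoints. If the two rules disagree once the data are unblinded, the plan does not settle which one holds. Applied as written, the Note could turn a clear day-113 benefit into a failed primary endpoint only because the benefit had appeared early and lasted.

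**Working it through.** **What the interaction tests.** Write Δ57, Δ85 and Δ113 for the active-minus-passive differences in mean change. The outcome is already change from baseline, and the Note ties VISIT to post-randomization assessments. The null of no interaction is therefore Δ57 = Δ85 = Δ113. The primary null is Δ113 = 0. Neither implies the other.

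**The plan's own power figure.** RCT SAP section 4 gives 83 per arm, 2.64 points on MDS-UPDRS Part I, SD 5.32, 2-sided 0.05 and 89.2% power.
- SE = 5.32 × √(2/83) = 0.826, and 2.64/0.826 = 3.197.
- Φ(3.197 − 1.960) = 89.2%. The figure reproduces.

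This is a simple two-group comparison of change, so the trial was sized for the visit contrast and not for an interaction.

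**Inputs for the comparison**
- From RCT SAP section 4: 83 per arm, a 35-point MDS-NMS effect, SD 70.8. The SD is that of scores in a subgroup with Part I above 10, used here as an assumed SD of change. Footnote 2 expects the SD for the whole sample to be lower.
- Assumed, not in the documents: equal correlation ρ of 0.3 to 0.8 between visits, the effect profiles below, no dropout, no site term.

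**Day-113 contrast.** SE = 70.8 × √(2/83) = 10.99, and 35/10.99 = 3.185. The noncentral t with 164 df gives 93.7% at 1-sided 0.05 (88.6% at 1-sided 0.025). With 32.7 points and SD 65.87, power at 1-sided 0.05 is 93.8%.

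**Interaction, 2 df (VISIT categorical).** The noncentrality is λ = n × Σ(Δj − mean Δ)² / [2 × SD² × (1 − ρ)], referred to F with 2 and 163 df. For −25/−30/−35 at ρ = 0.5 the sum of squares is 50, so λ = 83 × 50 / (2 × 5012.64 × 0.5) = 0.828 and power is 11.6%.

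**Interaction, 1 df (linear VISIT, 1-sided for benefit).** The noncentrality is (Δ57 − Δ113) / [SD × √(4(1 − ρ)/n)], referred to t with 164 df. For the same profile at ρ = 0.5 it is 10/10.99 = 0.910 and power is 23.0%.

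Probability of declaring significance, over ρ = 0.3 to 0.8:

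| Effect at days 57/85/113 | Day-113 contrast | Interaction, 2 df | Interaction, 1 df |
|---|---|---|---|
| −35/−35/−35 | 93.7% | 5% | 5% |
| −25/−30/−35 | 93.7% | 10% to 23% | 19% to 42% |
| −12/−24/−35 | 93.7% | 33% to 84% | 55% to 95% |
| −35/−18/0 | 5% | 66% to over 99% | 0% |

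For a constant benefit Σ(Δj − mean Δ)² is zero, so the interaction stays at 5% whatever the SD, correlation or coding. Simulation of 20,000 trials at ρ = 0.3 and 0.8 agreed with the calculated values to within 0.6 percentage points.

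**Which profile is plausible.** The protocol expects some growth. In the pilot, "additional benefits were demonstrated in the second 4 weeks (28 days) of treatment relative to the first" (section 2.2.2), and section 4.3 says the response had not levelled off by week 8. A constant effect is thus a limiting case. A benefit already large at day 57 that then grows modestly (second row) fits that account, and the interaction usually misses it.

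**The case against.** The best defence is that the Note is only loosely worded. A finding at a given visit cannot come from an omnibus interaction, and a 2-df F test has no direction, so it cannot be the 1-tailed test in 7.7.1.1. The authors may have meant the arm difference at that visit taken from the ARM*VISIT term, which is the LSMean contrast. Sections 7.8.4.1 and 7.8.4.2 of the OLE SAP support that intent. RCT SAP 2.1 and 7.7.1.2 also frame the hypothesis and success as a comparison of the arms after 12 weeks. The fourth row of the table would not meet that description of success.

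This is plausible as intent, but it is not what the sentence says. Sections 2.1 and 7.7.1.2 do not name the test that makes a reduction statistically significant. The Note does, and it names the wrong one.

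Two further points carry some weight. The 1-df form is the less natural reading: SITE also has one coefficient although it is nominal, so single coefficients are probably shorthand. The power figures also depend on the SD. With an assumed SD of change of 50 or 40, the steep profile reaches 60% to 99% or 80% to over 99% (2 df). The partly gradual profile reaches 15% to 42% or 21% to 61% (2 df), and 29% to 65% or 39% to 81% (1 df). The documents give no such SD. At the SAP's own 70.8 the partly gradual benefit is mostly missed, and the 5% for a constant benefit does not depend on the SD at all.

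**Conclusion.** The concern holds: the Note states a wrong significance rule for the gatekeeping primary endpoint, and it conflicts with the visit contrast in the same section. Under the assumptions listed, a 35-point day-113 benefit has 93.7% power by the contrast. By the interaction it has 5% if the benefit is constant, and 10% to 23% (2 df) or 19% to 42% (1 df) if it grows from 25 to 35 points. The two rules come close only when the effect rises steeply and visits are highly correlated, or when the SD of change is well below the SAP's figures. The sizes rest on assumed correlations, profiles and SD; the conflict in the text does not. This must be fixed.

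**What to change.** Delete the interaction sentence from the Note in RCT SAP 7.7 and put in its place:

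> Statistical significance of the primary endpoint is determined by the active-minus-passive LSMean contrast at day 113 from the MMRM, 1-sided as in section 7.7.1.1. VISIT is categorical. ARM*VISIT stays in the model and is not a success criterion.

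Use parallel wording at day 112 for MDS-UPDRS II and PDQ-39SI. In the OLE SAP, add one line confirming that the LSMean contrast at EOT1 also decides the OLE primary endpoint, in keeping with 7.8.4.1 and 7.8.4.2.

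The cost is one replaced passage in the RCT SAP, with its parallel wording, and one added line in the OLE SAP. Nothing changes in data collection, power or resources. If the authors meant the visit contrast all along, the edit only records that.

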7.6. ANALYSIS OF TREATMENT GROUP COMPARABILITY

An evaluation of treatment group characteristics will be compared across the two treatment arms. The characteristics will include demographics, baseline disease characteristics, concomitant medications, scores in outcome measures at baseline. Descriptive statistics will be presented by treatment groups. Differences in baseline scores will be determined using parametric or non-parametric approaches as appropriate based upon visual inspection of the distribution. Categorical variables will be summarized using frequencies and percentages. Baselines will be considered different in circumstances where p < 0.05. Numbers of early withdrawals will be compared across treatment arms using Fisher's exact test. Reasons provided for early post-randomization withdrawals will be reported. Withdrawals due to similar adverse events will be grouped into categories. Fisher's exact tests stratified by category will then be conducted to determine if there is an association between the number of subjects experiencing withdrawal due to adverse events and treatment arm.

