7.7.2.1. Combined measure of MDS-UPDRS Parts I, II, and III (sum score)

This endpoint will evaluate the change in the combined measure of MDS-UPDRS Parts I, II and III at the end of the treatment period (day 112 and 113), which is defined based on the change relative to baseline (days 28/29) scores to provide a measure of global function in PD. This outcome will support that TNM[™] Device treatment provide clinically meaningful changes for people with PD. Changes meeting or exceeding the previously established MCID for this measure (-6.7 points for clinical improvement) (Makkos, Kovacs et al. 2018) will be considered clinically meaningful. MDS-UPDRS Part II.

This endpoint will evaluate the change in MDS-UPDRS part II score at the end of the treatment period (day 112) relative to baseline (mean of day 0 and day 28) scores. Changes will be considered to be clinically meaningful if the mean difference (if normal distribution) or median difference (if non-normal distribution) meets or exceeds the previously established MCID (-3.05 for clinical improvement) (Horvath, Aschermann et al. 2017).

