7.7.2.3. MDS-UPDRS Part III

This endpoint will evaluate the change in MDS-UPDRS Part III score at the end of the treatment period (day 113) relative to the baseline (day 29) score. Changes will be considered to be clinically meaningful if the mean/median difference meets or exceeds the previously established MCID (-3.25 for clinical improvement) for this scale (Horvath, Aschermann et al. 2015).

This analysis will be derived only from the ON-state MDS-UPDRS Part III: motor exam scores, and MDS-UPDRS Part III data collected in the OFF-state will not be included in any analysis. The scores will be provided by blinded central raters when available except for scores from item 3 (related to rigidity). Scores for items related to rigidity will be derived from the blinded local rater scores when calculating the MDS-UPDRS part III score. Additionally, the ability of the centralized raters to provide scores will depend on the availability of quality video feed captured by the clinical sites. Video will be captured by Machine Medicine's Kelvin-PD software which was selected by the Sponsor to minimize the risk of video capture that is of inadequate quality for accurate centralized rating. However, it is possible that some video data may be missing or of poor quality, and thus, cannot be rated by a central rater. In cases where MDS-UPDRS Part III data from central raters from either the baseline or the end of treatment visit cannot be scored by the central rater, scores provided by the local raters will be utilized for both the baseline and end of treatment assessments. In cases where the last assessment was captured remotely using telemedicine platforms, the score will be prorated to the scale of the in-clinic MDS-UPDRS Part III. Additionally, the day 0 baseline measure (virtual visit) will be prorated to the scale of the in-clinic MDS-UPDRS Part III will be substituted for the baseline value. This will only occur if a virtual visit is required due to the participant's inability to travel to the site for the end of treatment visit.

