7.10.4. Study blind

Although unlikely, it is possible that knowledge of the study Sponsor and Device name may have the potential to unblind participants or bias them with regard to their expectation of treatment effect. Therefore, the study Sponsor excluded this information from informed consent documents. However, a subset of local institutional review boards and ethics committees required that the Sponsor name be included in the informed consent forms given to the participants at their site. To determine if having the name of the Sponsor in

the informed consent alters the effect of the device, the same modeling methodology used for the efficacy analysis described above will be utilized to determine the effect of having knowledge of the Sponsor name on efficacy, specifically, MMRM will be utilized separately for participants treated at sites where the Sponsor name was included in the ICF vs not included in the ICF. The results of this analysis will be used to determine if knowledge of the Sponsor name affects the relationship between treatment (active or passive) and each outcome. This analysis will be conducted for primary and secondary outcomes.

7.10.5. Comparison to baseline 2

For the primary outcome (at minimum), a confirmatory sensitivity analysis will be conducted to evaluate change in the primary outcome relative to scores obtained during the second baseline assessment only.

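### RCT efficacy models adjust for baseline only if the arms differ at p < 0.05; otherwise the baseline slope is fixed at 1, which mis-corrects chance imbalance unless the true slope is 1

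*SAP*

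**What the plan says.** The RCT SAP is Appendix 1 of the OLE SAP. Its section 7.7 gives two models: an MMRM for outcomes with several post-randomisation visits and a linear model for outcomes with one. In both, the response is the follow-up score minus baseline. The default terms are arm and site, plus visit and arm-by-visit in the MMRM, with no baseline term. For each model the section then adds: "An effect for baseline value will be included for outcomes where the baseline scores significantly different between the treatment arms".

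Section 7.6 defines the trigger: "Baselines will be considered different in circumstances where p < 0.05". The type of test is left open, to be chosen from "parametric or non-parametric approaches as appropriate based upon visual inspection of the distribution".

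The baseline itself differs by outcome:
- MDS-NMS total (primary, 7.7.1): "relative to baseline (mean of day 0 and day 29) scores".
- MDS-UPDRS Part II and PDQ-39SI: "relative to baseline (mean of day 0 and day 28) scores".
- MDS-UPDRS Part III (7.7.2.3): "relative to the baseline (day 29) score".
- Combined Parts I, II and III (7.7.2.1): "which is defined based on the change relative to baseline (days 28/29) scores".

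Randomisation is stratified by site only (section 3), so the design does not balance baseline score. Section 7.10.5 adds a sensitivity analysis for change "relative to scores obtained during the second baseline assessment only", which alters the baseline that is subtracted but adds no covariate. Nothing else in the RCT SAP or protocol restores adjustment.

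**The concern.** A change score without a baseline term forces the slope of follow-up on baseline to be 1. If the true slope is b and the arms differ at baseline by chance by D, the treatment contrast is off by (1 − b)D. With b below 1, the arm that starts worse is flattered; with b above 1, the arm that starts better is.

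A significance test between randomised arms measures chance. It does not measure whether baseline predicts outcome, so it is the wrong basis for choosing the model. The rule leaves every imbalance short of p = 0.05 with the fixed slope. At stake is the interpretation of one realised trial: with a moderate imbalance, the chance of a positive result depends on which arm happened to start worse. A smaller point is that the model choice also depends on which baseline test is picked after looking at the distribution.

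**Working it through.** **The plan's own figure.** RCT SAP section 4: 83 completers per arm, difference 2.64, SD 5.32, two-sided 0.05. 2.64 / (5.32 × √(2/83)) = 3.197; 3.197 − 1.96 = 1.237; power = Φ(1.237) = 89.2%, as stated. The documents give no figure for the baseline rule.

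**Inputs.** From the RCT SAP: 83 per arm; MDS-NMS SD 70.8; planning MCID 32.7 to 35.4 points (section 4); one-sided α = 0.05 (7.7.1.1). Assumed, because the documents do not give them: r, the correlation between any two visits (0.3 to 0.9), and k, follow-up SD divided by single-visit baseline SD (0.9 to 1.2). Site and interim visits are ignored.

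**Slope.** In units of single-visit baseline variance, V = (1 + r)/2 for a mean of two baselines and V = 1 for one. The true slope is b = rk/V, so b = 1 only when k = V/r:

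| r | 0.5 | 0.7 | 0.8 | 0.9 |
|---|---|---|---|---|
| k for slope 1, averaged baseline | 1.50 | 1.21 | 1.13 | 1.06 |
| k for slope 1, single baseline | 2.00 | 1.43 | 1.25 | 1.11 |

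**MDS-NMS bias at the threshold.** Imbalance at p = 0.05: D = 1.96 × 70.8 × √V × √(2/83). For r = 0.7, k = 1.0: V = 0.85, D = 19.9 points, b = 0.7/0.85 = 0.824, bias = 0.176 × 19.9 = 3.5 points. In the same way:

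| r (D, points) | k = 1.0 | k = 1.1 | k = 1.2 |
|---|---|---|---|
| 0.5 (18.7) | 6.2 | 5.0 | 3.7 |
| 0.7 (19.9) | 3.5 | 1.9 | 0.2 |
| 0.8 (20.4) | 2.3 | 0.5 | −1.4 |

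**Conditional type I error.** For each setting, 400,000 trials were simulated. The SAP rule was a change-score t-test, replaced by ANCOVA if the baseline t-test gave p < 0.05; the comparator was ANCOVA always. Condition: null true, active arm worse at baseline with |z| from 1.2 to 1.97 (two-sided p 0.23 to 0.05), which is 9.1% of trials. Rejection under the SAP rule, in %, for r = 0.5 / 0.7 / 0.8:

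| k | Averaged baseline | Single baseline |
|---|---|---|
| 0.9 | 13.8 / 12.1 / 11.9 | 17.0 / 15.2 / 14.1 |
| 1.0 | 11.3 / 9.2 / 8.7 | 15.5 / 12.5 / 11.0 |
| 1.1 | 9.2 / 7.0 / 5.6 | 13.1 / 10.2 / 8.2 |
| 1.2 | 8.0 / 5.3 / 3.6 | 11.7 / 8.2 / 5.8 |

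Monte Carlo SE is at most about 0.2 points. Always adjusting gave 4.8 to 5.2%. In the mirror 9.1% of trials (active arm better, k = 1.0) the SAP rule gave 1.3 / 2.0 / 2.5% averaged and 0.3 / 0.8 / 1.3% single. At r = 0.9 with an averaged baseline, the active-worse figure is 7.0% (k = 1.0), 3.7% (k = 1.1) and 1.7% (k = 1.2), so the direction reverses.

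**Conditional power.** Effect 2.64/5.32 of the change-score SD, active arm better by |z| 1.2 to 1.97, k = 1.0, r = 0.5 / 0.7 / 0.8. Averaged baseline: 86.5 / 88.5 / 89.9% under the SAP rule against 95.7 / 94.6 / 94.1% adjusted. Single baseline: 81.8 / 84.9 / 86.8% against 97.8 / 96.2 / 95.3%.

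**Over all randomisations.** Type I error is 4.2 to 5.1% under the SAP rule and 5.0 to 5.1% always adjusted. The average power gain from adjusting at k = 1.0 is 0.1 to 2.5 points (averaged) and 0.8 to 4.1 points (single).

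**The case against.** A prespecified change-score analysis is valid: over randomisation it is unbiased and its type I error is controlled. The excess of false positives when the active arm starts worse is offset by a deficit when it starts better. This stands, and it limits the point to conditional behaviour and some precision.

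The power loss for the primary endpoint also depends on how the effect is scaled. Setting it at 2.64/5.32 of the change-score SD follows section 4, which tests mean change scores with SD 5.32. For MDS-NMS, however, the same section applies that ratio to a score SD of 70.8, giving 35.1 points. At 35.1 points, in the same active-better band (averaged baseline, k = 1.0), power is 94.6% against 98.7% adjusted at r = 0.5, 99.8% against 99.9% at r = 0.7, and about 100% for both at r = 0.8. The average gain is then about 0.7 points at r = 0.5 and under 0.1 at r = 0.7 or above. On that scale, loss of power is not a strong reason to change the primary analysis.

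Size and direction rest on r and k, which are unknown, and the largest figures concern secondary endpoints that count only if MDS-NMS succeeds. Both statements are true. But the combined MDS-UPDRS score has a single baseline and is the first secondary in the fixed sequence (7.7.2), so its result decides whether any later endpoint can be claimed. Not knowing the slope argues for estimating it.

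**Conclusion.** The concern holds. The rule is explicit, applies to both RCT models, and is not undone elsewhere. A fixed slope of 1 mis-corrects chance imbalance unless the true slope is 1, and the documents do not give the quantities needed to tell. The harm is conditional: across the tabulated settings, the false-positive rate with a moderately worse active arm runs from 3.6% to 13.8% for averaged-baseline outcomes and from 5.8% to 17.0% for single-baseline outcomes, against about 5% with adjustment. For MDS-NMS, the bias at the threshold is at most 6.2 points over the tabulated r and k, against a planning MCID of 32.7 to 35.4. Overall type I error is not at risk. Confidence is high in the existence of the rule and the validity of always adjusting; size and direction depend on the assumed r and k. This should be changed because the correction costs almost nothing and makes the result insensitive to which arm starts worse.

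**What to change.** In RCT SAP 7.7, delete both conditional sentences and write, for example: *For the RCT between-arm analyses, the baseline value will be a fixed covariate (with baseline-by-visit in the MMRM) for every continuous outcome that has a baseline score, irrespective of any test of baseline difference.* This covers MDS-NMS, the combined MDS-UPDRS score, Part II, Part III and PDQ-39SI. Overall CGI-I is outside it, being a direct rating of change with no baseline score. Make the 7.6 baseline comparisons descriptive only, which also removes the dependence on the choice of test.

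OLE SAP 7.8 imports RCT SAP 7.7, so add a sentence there that this covariate rule is for the RCT between-arm analyses and does not carry over automatically. The similar p < 0.05 rule in OLE SAP 7.7.1 should also become one prespecified choice. That needs its own justification, because the OLE baseline is the RCT end-of-treatment score (OLE SAP 7.4) and so is also the passive-period outcome; no particular choice is proposed here.

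Cost: wording in RCT SAP 7.6 and 7.7, one model term with its visit interaction, one sentence in OLE SAP 7.8, and a separate decision for OLE SAP 7.7.1. No new data.
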